4.2 Discussion of Study Design

Choice of Control Group

Placebo control will be used in this study to address potential confounding factors, such as placebo effect, potential investigator bias in safety and efficacy assessment, or regression to the mean in endpoint scoring.

Appropriateness of Measurements

Standard statistical, clinical, and laboratory procedures will be utilized in this study. All efficacy measurements in this study for assessing disease activity in adult subjects with moderate to severe PPPsO have been used in other studies assessing this subset of patients.^{11,15,16,26,27} All clinical and laboratory procedures in this study are standard and generally accepted. Patient-reported outcome (PRO) measures in this study were included to assess patient symptoms and quality of life.

Suitability of Subject Population

Female or male adults with chronic PPPsO with or without psoriatic arthritis for at least 6 months prior to Baseline and a ppIGA of "moderate" or "severe" (\geq 3, at Screening and Baseline) and who are

candidates for systemic therapy are eligible for this study. Eligible subjects must also have \geq 1% BSA PsO involvement, sPGA score of "moderate" or "severe" (\geq 3), PPASI \geq 8 (moderate or severe disease),²⁸ and at least 1 additional PsO plaque outside of the palms and soles at Screening and the Baseline visit. At least 50% of the overall study population will be comprised of subjects with Baseline BSA \geq 10%. The selection criteria relating to safety ensure that enrolled subjects can safely be treated with risankizumab based on the current knowledge of this drug.

Selection of Doses in the Study

The risankizumab dosing regimen selected for the current study (i.e., 150 mg SC at Weeks 0, 4, and q12w thereafter up to Week 40) is the same as used in the risankizumab pivotal Phase 3 studies in subjects with moderate to severe chronic plaque PsO. The risankizumab 150 mg SC dose has been shown to be efficacious with an acceptable safety profile and is considered appropriate for the treatment of subjects with plaque PsO.

5 STUDY ACTIVITIES

5.1 Eligibility Criteria

Subjects must meet all of the following criteria in order to be included in the study. Anything other than a positive response to the questions below will result in exclusion from study participation.

Consent

- 1. Subjects or their legally authorized representative must voluntarily sign and date an informed consent, approved by an independent ethics committee (IEC)/institutional review board (IRB), prior to the initiation of any screening or study-specific procedures.
- 2. Employees of the Sponsor and/or study sites and their family members may not be enrolled in this study.
- 3. Subjects must be willing and able to comply with procedures required in this protocol.

Demographic and Laboratory Assessments

- 4. Adult male or female, at least 18 years old (subjects must also meet the legal age of majority per local law).
- 5. Laboratory values meeting the following criteria within the Screening period prior to the first dose of study drug:
 - Serum aspartate aminotransaminase (AST) ≤ 2 × upper limit of normal (ULN);
 - Serum alanine aminotransaminase (ALT) ≤ 2 × ULN;
 - Serum total bilirubin ≤ 2.0 mg/dL; except for subjects with isolated elevation of indirect bilirubin relating to Gilbert syndrome;
 - Total white blood cell (WBC) count \geq 3,000/µL;
 - Absolute neutrophil count (ANC) \geq 1,500/µL;

- Platelet count \geq 100,000/µL;
- Hemoglobin \geq 10 g/dL (100 g/L).

Disease Activity

- 6. Female or male adults with chronic PPPsO (with or without psoriatic arthritis) for at least 6 months prior to Baseline and a ppIGA of "moderate" or "severe" (≥ 3), at Screening and Baseline.
- 7. Subjects must have at Screening and Baseline:
 - Plaque PsO BSA involvement of $\geq 1\%$,
 - sPGA score of "moderate" or "severe" (≥ 3),
 - PPASI \geq 8 (moderate or severe disease), and
 - At least 1 additional PsO plaque outside of the palms and soles.

At least 50% of the overall study population will be comprised of subjects with Baseline BSA \geq 10%.

- 8. Previously inadequately controlled disease by topicals, phototherapy, and/or systemic treatments.
- 9. Subject must be a candidate for systemic therapy as assessed by the investigator.

Subject History

- I0. Subject is judged to be in good general health, as determined by the investigator based upon the results of a medical history, physical examination, laboratory profile, and a 12-lead electrocardiogram (ECG) performed during the Screening period.
- 11. No forms of PsO other than chronic plaque-type PsO (e.g., pustular PsO, palmoplantar pustulosis, acrodermatitis of Hallopeau, erythrodermic, or guttate PsO).
- I2. No current drug-induced PsO or a drug-induced exacerbation of pre-existing psoriasis.
- 13. No active ongoing inflammatory skin diseases other than PsO and psoriatic arthritis that could interfere with the assessment of PsO (e.g., hyperkeratotic eczema).
- 14. Subjects must not have a history of clinically significant (per investigator's judgment) **drug or alcohol abuse** within the last 6 months.
- I5. Subjects must not have a history of an **allergic reaction** or significant sensitivity to constituents of the study drug (and its excipients) and/or other products in the same class.
- I6. Subjects must not have had **major surgery** performed within 12 weeks prior to randomization or planned during the conduct of the study (e.g., hip replacement, aneurysm removal, stomach ligation).
- I7. Subjects must not have evidence of:
 - Hepatitis B virus (HBV) or hepatitis C virus (HCV) infection, defined as:

- HBV: Hepatitis B surface antigen (HBs Ag) positive (+) test or detected sensitivity on the HBV DNA polymerase chain reaction (PCR) qualitative test for subjects who are hepatitis B core antibody (HBc Ab) positive (+) (and for hepatitis B surface antibody [HBs Ab] positive [+] subjects where mandated by local requirements).
- HCV: HCV RNA detectable in any subject with anti-HCV antibody (HCV Ab).
- Human immunodeficiency virus (HIV), defined as confirmed positive anti-HIV Ab test. Note: In case a screened subject has a confirmed positive HIV Ab test, Eligibility Criterion 10 (Subject is judged to be in good general health criteria...) should be selected in electronic case report form (eCRF) for documentation of screening failure.
- Active TB. For subjects with latent TB, please see Section 3.16 of the Operations Manual.
- Active systemic infection/Clinically important infection during the last 2 weeks prior to Baseline visit as assessed by the investigator.
- I8. Subject must not have any of the following medical diseases or disorders:
 - Recent (within past 6 months) cerebrovascular accident or myocardial infarction;
 - History of an organ transplant which requires continued immunosuppression;
 - Active or suspected malignancy or history of any malignancy within the last 5 years except for successfully treated non-melanoma skin cancer (NMSC) or localized carcinoma in-situ of the cervix.
- I9. Subject must not have concurrent clinically significant medical conditions other than the indication being studied or any other reason that the investigator determines would interfere with the subject's participation in this study, would make the subject an unsuitable candidate to receive study drug, or would put the subject at risk by participating in the study.
- 20. No known active severe acute respiratory syndrome coronavirus 2 (SARS-CoV-2) infection. If a subject has signs/symptoms suggestive of SARS-CoV-2 infection, they should undergo molecular (e.g., PCR) testing to rule out SARS-CoV-2 infection. In addition, if based on the answers to the SARS-CoV-2 Infection Risk Assessment Tool the site considers the subject currently at risk for developing SARS-CoV-2 infection, then the subject should either be tested or advised to come back for study screening after 14 days.

Subjects who do not meet SARS-CoV-2 infection eligibility criteria must be screen failed and may only rescreen after they meet the following SARS-CoV-2 infection viral clearance criteria:

• At least 14 days since first PCR test result have passed in asymptomatic patients or 14 days since recovery, defined as resolution of fever without use of antipyretics and improvement in symptoms.

Contraception

21. For all females of child-bearing potential; a negative serum pregnancy test at the Screening visit and a negative urine pregnancy test at Baseline prior to the first dose of study drug is required.

- 22. Female subjects of childbearing potential must practice at least 1 protocol-specified method of birth control, that is effective from Study Day 1 through at least 140 days (20 weeks or as guided by the local risankizumab label [if approved], whichever is longer) after the last dose of study drug (local practices may require 2 methods of birth control). Female subjects of non-childbearing potential do not need to use birth control.
- 23. Female subjects may not be pregnant, breastfeeding, or considering becoming pregnant during the study or for approximately 140 days (20 weeks or as guided by the local risankizumab label [if approved], whichever is longer) after the last dose of study drug.

Concomitant Medications (Prior Medication Restrictions)

- 24. No prior exposure to risankizumab.
- 25. Subject must not have received **any live viral or bacterial vaccine** within 4 weeks prior to the first dose of study drug, or expected need of live vaccination during study participation including at least 140 days (20 weeks or as guided by the local risankizumab label [if approved], whichever is longer) after the last dose of study drug.
- 26. Subject must not have been treated with **any investigational drug** within 30 days or 5 half-lives of the drug (whichever is longer) prior to the first dose of study drug or is currently enrolled in another clinical study or was previously enrolled in this study.
- 27. Subject did not receive any systemic biologics to treat PsO for the following timeframes prior to the Baseline visit:
 - Etanercept (Enbrel[®]) and biosimilar versions within 3 weeks;
 - Certolizumab (Cimzia[®]), adalimumab (Humira[®]), ixekizumab (Taltz[®]), brodalumab (Siliq[®]/Kyntheum[®]), infliximab (Remicade[®]), and biosimilar versions within 10 weeks;
 - Ustekinumab (Stelara[®]) and guselkumab (Tremfya[®]) within 15 weeks;
 - Tildrakizumab (Ilumya[™]) and secukinumab (Cosentyx[®]) within 20 weeks.
- 28. Subject did not receive for at least 30 days prior to randomization any:
 - Other systemic immunomodulating treatments (including, but not limited to: e.g., methotrexate, cyclosporine A, corticosteroids, cyclophosphamide, tofacitinib [Xeljanz[®]], apremilast [Otezla[®]]);
 - Other systemic PsO treatments (e.g., retinoids, fumarates, any other drug known to possibly benefit PsO);
 - Photochemotherapy (e.g., psoralen and ultraviolet A radiation [PUVA]), phototherapy (e.g., ultraviolet B rays [UVB]).
- 29. Subject did not receive for at least 14 days prior to randomization any topical treatment for PsO or any other skin condition (including, but not limited to: e.g., corticosteroids, vitamin D analogues, vitamin A analogues, pimecrolimus, retinoids, salicyl vaseline, salicylic acid, lactic acid, tacrolimus, tar, urea, or anthralin).

5.2 Contraception Recommendations

Contraception Requirements for Females

Subjects must follow the following contraceptive guidelines as specified:

• Females, Non-Childbearing Potential

Females do not need to use birth control during or following study drug treatment if considered of non-childbearing potential due to meeting any of the following criteria:

- Premenopausal female with permanent sterility or permanent infertility due to one of the following:
 - Permanent sterility due to a hysterectomy, bilateral salpingectomy, bilateral oophorectomy.
 - Non-surgical permanent infertility due to Mullerian agenesis, androgen insensitivity, or gonadal dysgenesis; investigator discretion should be applied to determining study entry for these individuals.
- Postmenopausal, female:
 - Age > 55 years with no menses for 12 or more months without an alternative medical cause.
 - Age ≤ 55 years with no menses for 12 or more months without an alternative medical cause AND a follicle-stimulation hormone (FSH) level > 30 IU/L.
- Females, of Childbearing Potential
 - Females of childbearing potential must avoid pregnancy while taking study drug(s) and for at least 140 days (20 weeks or as guided by the local risankizumab label [if approved], whichever is longer) after the last dose of study drug.
 - Females must commit to one of the following methods of birth control:
 - Combined (estrogen- and progestogen- containing) hormonal birth control (oral, intravaginal, transdermal, injectable) associated with inhibition of ovulation initiated at least 30 days prior to study Baseline.
 - Progestogen-only hormonal birth control (oral, injectable, implantable) associated with inhibition of ovulation initiated at least 30 days prior to study Baseline.
 - Bilateral tubal occlusion/ligation (can be via hysteroscopy, provided a hysterosalpingogram confirms success of the procedure).
 - Intrauterine device (IUD).
 - Intrauterine hormone-releasing system (IUS).
 - Vasectomized partner (provided the partner has received medical confirmation of the surgical success of the vasectomy and is the sole sexual partner of the trial subject).
 - Practice true abstinence, defined as: Refraining from heterosexual intercourse when this is in line with the preferred and usual lifestyle of the subject (periodic abstinence

[e.g., calendar, ovulation, symptothermal, post-ovulation methods] and withdrawal are not acceptable).

If required per local practices, male or female condom with or without spermicide OR cap, diaphragm or sponge with spermicide should be used in addition to one of the birth control methods listed above (excluding true abstinence).

Contraception recommendations related to use of concomitant therapies prescribed should be based on the local label.

5.3 Prohibited Medications and Therapy

- 1. During the study, no biologic treatment is allowed. Exception: Treatment with commercially available risankizumab after the Week 52/Premature Discontinuation (PD) assessments if this has been determined as an appropriate subsequent treatment by the investigator in discussion with the subject.
- 2. Systemic (including oral or injectable administrations) non-biologic therapy that can be used to treat PsO, including but not limited to cyclosporine, corticosteroids, methotrexate, retinoids, apremilast, and fumaric acid derivatives.
- 3. Phototherapy treatment (UVB or ultraviolet A [UVA] phototherapy, including PUVA), laser therapy, tanning booth, or extended sun exposure that could affect disease severity or interfere with disease assessments.
- 4. Topical PsO treatments, including but not limited to corticosteroids, anthralin, calcipotriene, topical vitamin D derivatives, retinoids, urea, α- or β-hydroxyl acids, and medicated shampoos (for example those that contain corticosteroids, coal tar, or vitamin D3 analogues).
- 5. All other investigational drugs and enrollment in another clinical study are prohibited.
- 6. Live attenuated vaccines are not permitted during study participation and including up to 140 days (20 weeks or as guided by the local risankizumab label [if approved], whichever is longer) after the last dose of study drug. Examples of live attenuated vaccines include, but are not limited to, the following:
 - Bacille Calmette-Guérin (BCG)
 - Zoster vaccine live (Zostavax[®])
 - Measles mumps rubella or measles mumps rubella varicella
 - Monovalent live attenuated influenza A (intranasal)
 - Oral polio vaccine
 - Rotavirus
 - Seasonal trivalent live attenuated influenza (intranasal)
 - Smallpox
 - Oral typhoid vaccine

- Varicella (chicken pox)
- Yellow fever
- Dengue (Dengvaxia[®])

5.4 Prior and Concomitant Therapy

Stable doses of concomitant therapies for chronic conditions, for which neither the condition nor the treatment are judged to exclude the patient from participation are permissible. All concomitant medications should be carefully evaluated by the investigator.

Any medication or vaccine (including over-the-counter or prescription medicines, vitamins, and/or herbal supplements) that the subject has received from 4 weeks prior to Screening or receives during the study must be recorded along with the reason for use; date(s) of administration, including start and end dates; and dosage information including dose, route, and frequency on the appropriate eCRF.

A detailed history of all prior biologic use will be obtained in the electronic data capture (EDC).

Any questions regarding concomitant or prior therapy should be raised to the AbbVie emergency contact. Information regarding potential drug interactions with risankizumab can be located in the risankizumab Investigator's Brochure.¹⁷

Subjects must be able to safely discontinue any prohibited medications (including biologics) 5 half-lives or 4 weeks, whichever is longer, prior to initial study drug administration. Subjects must be consented for the study prior to discontinuing any prohibited medications for the purpose of meeting study eligibility.

Non-live vaccines may be administered during screening or treatment period, if not contraindicated or medically inappropriate.

When possible, first dose of study drug should be given at least \pm 7 days from non-live SARS-CoV-2 vaccine administration. The potential impact of risankizumab on SARS-CoV-2 vaccination is unknown. The decision to receive a locally available non-live vaccine should be based on local guidance and an individual discussion between the treating physician and the subject and/or guardian.

Allowed Concomitant Medications/Therapy

Allowed concomitant medications and therapies include the following:

- Moisturizers: Provided that moisturizers (without active ingredients) have been used for at least 2 weeks prior to Baseline and are anticipated to be continuously used at least until the Week 16 visit. Subjects should not apply emollients within 8 hours prior to study assessments.
- Only inhaled, topical ophthalmic, or intranasal corticosteroids are permitted during the study.

COVID-19 Pandemic-Related Vaccination Guidance

Any SARS-CoV-2 vaccine information must be documented on the COVID-19 vaccine eCRF. Refer to the Operations Manual (Appendix F) for instructions on reporting any AEs associated with the COVID-19 vaccine.

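### Does the four-week stopping interval in Protocol 5.4 clash with the shorter etanercept and topical windows in criteria 27 and 29?

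*Protocol*

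**What the plan says.** Two parts of the Protocol deal with stopping earlier treatment.

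Section 5.4 gives one general interval: "Subjects must be able to safely discontinue any prohibited medications (including biologics) 5 half-lives or 4 weeks, whichever is longer". The sentence ends "whichever is longer, prior to initial study drug administration". The next sentence reads: "Subjects must be consented for the study prior to discontinuing any prohibited medications for the purpose of meeting study eligibility". The same section also gives a route for doubtful cases: "Any questions regarding concomitant or prior therapy should be raised to the AbbVie emergency contact".

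Section 5.1 opens its numbered list with "Subjects must meet all of the following criteria in order to be included in the study". Three of its prior-medication criteria set windows by drug or class:

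- Criterion 27 covers systemic biologics used for psoriasis and names ten of them. Etanercept has the shortest window: "and biosimilar versions within 3 weeks". The other nine have 10, 15 or 20 weeks.
- Criterion 28 sets 30 days for other systemic treatments and phototherapy.
- Criterion 29 covers topicals: the subject must not have received "for at least 14 days prior to randomization any topical treatment for PsO or any other skin condition".

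Section 5.3 prohibits biologics (item 1) and topical psoriasis treatments (item 4), so on a literal reading both fall under the general interval in 5.4. Neither section refers to the other on this point. The Operations Manual (Appendix F), which holds procedural detail, is not among the documents reviewed.

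**The concern.** Because the longer of the two limbs in 5.4 applies, the interval can never be less than 4 weeks. A subject who stopped etanercept 3 weeks before Baseline, or a topical 14 days before randomization, would satisfy the numbered criteria and still fall short of 5.4. Two sites could treat the same subject differently: one could randomize at once while the other waited.

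Three consequences seem possible:

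- Residual effect of earlier treatment could enter the Baseline assessment or the Week 16 response.
- Some eligible subjects could be delayed.
- The count in SAP Appendix A of subjects who entered without satisfying the entry criteria could depend on which passage the programmer takes as the rule.

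**Working it through.** The plan gives no computed figure here, so the check compares day counts and then traces each possible consequence.

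**Common end point.** Criterion 27 counts back from the Baseline visit, criteria 28 and 29 from randomization, and Section 5.4 from first dose. Protocol 4.1 places randomization and the first dose at the Baseline visit, and the Activity Schedule labels that visit Day 1. The intervals can therefore be compared directly.

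**Day counts.** The fixed limb of 5.4 is 4 × 7 = 28 days. The difference is the 5.1 window minus 28.

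| Window in 5.1 | Days | Difference from 28 |
|---|---|---|
| Etanercept, 3 weeks | 21 | 21 − 28 = −7 |
| Topicals | 14 | 14 − 28 = −14 |
| Criterion 28 treatments | 30 | 30 − 28 = +2 |
| Five biologics, 10 weeks | 70 | 70 − 28 = +42 |
| Two biologics, 15 weeks | 105 | 105 − 28 = +77 |
| Two biologics, 20 weeks | 140 | 140 − 28 = +112 |

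Against the 4-week floor, only etanercept and topicals fall short. The subjects concerned are those with last etanercept about 21 to 27 days before Day 1 (22 to 27 if day 21 still counts as inside the window), or last topical use 14 to 27 days before. The half-lives limb cannot be checked because the documents give no half-lives. It can only lengthen the 5.4 interval.

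**Recruitment.** Screening runs up to 35 days. A subject who stops at a screening visit on Day −35 has 35 − 28 = 7 days to spare under the 4-week floor. The extra wait is at most 7 days for etanercept and 14 for topicals, and nothing for a subject already off treatment for 28 days. Protocol 5.8 also provides for rescreening. The floor by itself need not turn anyone away.

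**Treatment comparison.** The interval concerns treatment before randomization, which is 1:1 and central. Any residual effect of earlier therapy is therefore balanced between arms in expectation. The severity thresholds (ppIGA and sPGA of at least 3, PPASI of at least 8) must be met at both Screening and Baseline whatever the interval. Absolute response rates might still shift, by an amount the documents do not allow to be estimated, but a shift of that kind is not between-arm bias.

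**Analysis sets.** Protocol 7.2 and SAP 4.0 define the ITT Population as all randomized subjects and use it for all efficacy analyses. There is no per-protocol set. Reclassifying a subject's washout cannot remove that subject from an efficacy analysis.

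**Deviation count.** SAP Appendix A refers to entry criteria, which most naturally means the numbered list in 5.1. The count differs only if the 5.4 sentence is read as a further entry criterion. Section 5.4 has medications recorded from 4 weeks before Screening, which covers the whole 14-to-27-day range before Day 1. The affected subjects could be identified from data already collected.

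**The case for a change.** The best case for a change starts from the wording. Section 5.4 is phrased as an obligation, fixes an interval that ends at first dose, and is followed by a sentence linking discontinuation to eligibility. It names biologics expressly, although criterion 27 already treats them drug by drug, and it makes no exception for 5.1. A careful site could reasonably read it as a second washout test. Protocol 5.9 makes investigators responsible for complying with all protocol requirements and for reporting deviations, so the reading could matter for reporting even if 5.4 is not an entry criterion. A clarification would take only a sentence or two.

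Much of this stands. The intervals differ, no statement of precedence appears, and the reading that specific windows apply to named drugs while the general interval covers the rest is an inference. That inference has support. Criterion 27 is limited to biologics given for psoriasis, whereas 5.3 bars all biologics and subjects with psoriatic arthritis may enrol, so a general interval has work to do for products and uses without their own window. The topical half of the conflict is weaker still, because an interval framed in half-lives fits systemic drugs more readily. Section 5.4 also sends questions on prior therapy to a sponsor contact, and the Operations Manual may settle the point.

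What does not follow is a consequence for the results. The case for change identifies no bias, no loss of power and no safety gain. Its remaining effect is on how some deviations are labelled.

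**Conclusion.** The concern is right about the wording but does not call for a change to the plan. The shortfalls are 7 days for etanercept and 14 for topicals against the 4-week floor. The texts can be satisfied together, and the trial as planned gives a sound comparison under either reading. The most that could move is the entry-criteria count in SAP Appendix A, and only on the less natural reading of that item. The number of subjects in the gap is unknown.

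This rests on Baseline, randomization and first dose all falling on Day 1 as planned, on all randomized subjects being analyzed, and on the half-lives limb being left aside for want of figures. The two passages must be reconciled as a matter of drafting. Which interval should stand is for the sponsor, and nothing here favours either.
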